Appendix 2. Approximate Equivalent Morphine Doses of Opioid Analgesics

Common opioid analgesics

Drug	Maximum Allowed Total Daily Dose	Relative potency to oral morphine	Half-Life
Morphine	0.2-0.5 mg/kg/dose, up to 15 mg/dose. No more than 5 doses/day.	1	1.5-4 hrs
Hydromorphone (Dilaudid)	0.03-0.08 mg/kg/dose, up to 2 mg/dose. No more than 5 doses/day.	4	2.5 hrs
Codeine (Paveral, Tylenol #2 and #3)	0.5-1.0 mg/kg/dose, up to 60 mg/dose. No more than 5 doses a day.	0.15	2.5-3.5 hrs
Oxycodone [Roxicodone; Percocet, Tylox]	0.05-0.15 mg/kg/dose, up to 5 mg/dose. No more than 5 doses a day.	~2	3.2 hrs

Sites should contact project team for acceptable alternative preparations and related data.

Lexi Comp Pediatric Dosage Handbook 15th Edition
Sick Kids Drug Handbook & Formulary 2008-2009
Rx Files Pediatric Pain: Treatment Considerations, Q & A's. Oct. 08

Appendix 3. Permitted Adjustments In JIA Therapies for Worsening Disease

The following adjustments of background medications are allowed for reasons of inadequate efficacy of current treatment, or may be tapered or discontinued due to disease improvement. Adjustments for safety reasons may be done at any time, but if this leads to changes in excess of those allowed below, the investigator must receive approval from the Pfizer project team to allow the subject to continue in the trial. Adjustment in background meds due to disease improvement can begin upon enrollment in this study.

1. NSAIDs/COX-2 inhibitors: dose adjustments may be made, or background NSAID/COX-2 inhibitors may be switched but should be more than 14 days prior to a study visit.
2. Oral corticosteroid dose should not exceed 0.20 mg/kg/day or 10 mg/day, prednisone or equivalent daily, whichever is lower. For subjects coming from the systemic JIA study A3921165, a higher prednisone-equivalent dose may be continued or started (doses must be \leq 1.0 mg/kg/day up to 30 mg/day oral prednisone [or equivalent]).
3. Methotrexate (\leq 20 mg/m²/week or 25 mg/week, whichever is lower), leflunomide (10 mg every other day for body weight of $<$ 20 kg; 10 mg every day for body weight of 20 to 40 kg; 20 mg every day for body weight of $>$ 40 kg; or as according to local standards) may be added and/or adjusted. Increases should be no more frequently than every month. Adjustments should be made more than 4 weeks prior to a study visit.
4. Sulfasalazine (\leq maximum recommended dose per local product information) may be adjusted. Increases should be no more frequently than every month. Adjustments should be made more than 4 weeks prior to a study visit. (Note: this only applies to subjects who enter the study on concomitant sulphasalazine since subjects may not start treatment with sulphasalazine while participating in A3921145).
5. Chloroquine (\leq maximum recommended dose per local product information) and hydroxychloroquine (\leq maximum recommended dose per local product information) should be adjusted no more frequently than every month. Adjustments should be made more than 8 weeks prior to a study visit. (Note: this only applies to subjects who enter the study on concomitant chloroquine or hydroxychloroquine since subjects may not start treatment with chloroquine or hydroxychloroquine while participating in A3921145).
6. Intra-articular steroid (eg, triamcinolone (KENALOG[®], Aristospan[®])) should be administered to no more than four joints in any given 6 month period and individual joints should not be injected any more frequently than once in a 6-month period. Injected joints will be considered as not assessed during the remainder of the study. Intra-articular injections should be avoided during the 6 weeks prior to a study visit.

A UNIFORM TAPERING OF A MEDICATION OR TITRATING UP ON A DOSAGE OF MEDICATION TOWARD A SPECIFIC PRE-DETERMINED GOAL DOSAGE (INCLUDING DISCONTINUATION) WILL BE CONSIDERED A SINGLE CHANGE IF ACCOMPLISHED WITHIN 1 MONTH.

Appendix 4. Permitted Adjustments (Tapering) of JIA Medications for Subjects with Inactive Disease for at Least 24 Weeks

Subjects who have inactive disease for at least 24 consecutive weeks may begin to taper off of concomitant JIA therapies and tofacitinib. Tapering of therapies is to be completed in the following order: oral corticosteroids, MTX/leflunomide, tofacitinib.

- For subjects who are not taking concomitant oral corticosteroids, tapering will start with MTX/leflunomide, followed by tofacitinib.
- For subjects who are not taking concomitant MTX/leflunomide, tapering will start with oral corticosteroids, followed by tofacitinib.
- For subjects not taking concomitant oral corticosteroids or MTX/leflunomide, tapering will start with tofacitinib.

The rate at which each drug is tapered is described below.

Oral Corticosteroids: The dose of oral corticosteroids may be reduced or discontinued for subjects who have inactive disease for at least 24 consecutive weeks (time in parent study and A3921145 inclusive). The dose can be reduced by 0.1mg/kg each week. Once the dose of corticosteroids is at 5 mg/day then an absolute decrease by 1 mg/day each week can be implemented.

Methotrexate/leflunomide: The dose of MTX/leflunomide may be decreased or discontinued for subjects who continue to have inactive disease for at least 24 consecutive weeks after receiving the last dose of oral corticosteroids. MTX/leflunomide may be discontinued with or without tapering based on local practice; it is acceptable to stop the drug abruptly or by tapering the dose.

Tofacitinib: The dose of tofacitinib may be decreased or discontinued for subjects who continue to have inactive disease for at least 24 consecutive weeks after receiving the last dose of MTX/leflunomide. The dose is to be reduced by 5 mg every 12 weeks as long as the subject's disease remains inactive. The evening dose should always be reduced before the morning dose. For example, a subject receiving a total daily dose (TDD) of 10 mg (5 mg BID) prior to tapering will step down to a TDD of 5 mg by taking 5 mg in the morning and 0 mg in the evening. If they continue to have inactive disease for a least 12 consecutive weeks while receiving a TDD of 5 mg, the 5 mg morning dose may also be discontinued.

Subjects will be followed for 6 months (24 weeks) after tofacitinib is discontinued by returning to the site for schedule visits and completing all visit assessments.

If at any time during the tapering process or after discontinuation of tofacitinib, the subject is not able to maintain the inactive disease status (as defined in the protocol [Section 7.1.7](#)), concomitant JIA therapies (eg, oral corticosteroid, methotrexate/leflunomide) and tofacitinib can resume if appropriate according to investigator judgment.

Tofacitinib will restart at 5 mg BID. Concomitant JIA therapies and doses should be adjusted at the discretion of the investigator.

Appendix 5. Estimated Glomerular Filtration Rate (GFR) and Creatinine Clearance (CrCl) Calculations

1. eGFR will be evaluated at screening to determine if a subject is eligible.

The Bedside Schwartz GFR equation²¹ will be used to estimate glomerular filtration rate (eGFR) from serum creatinine (creatinine methods with calibration traceable to IDMS).

$$\text{eGFR (mL/min/1.73 m}^2\text{)} = 0.413 \times (\text{Ht} / \text{Scr})$$

Height (Ht) in cm;

Serum creatinine (Scr) in mg/dL

2. Creatinine clearance (CrCl) will be evaluated at every study visit.

- (i) Participants <12 years of age

The Modified Schwartz equation²⁷ will be used to estimate creatinine clearance in participants < 12 years of age

$$\text{CrCl (mL/min/1.73 m}^2\text{)} = (\text{K} \times \text{Ht}) / \text{Scr}$$

K (proportionality constant):

Female Child < 12 years of age: K = 0.55

Male Child < 12 years of age: K = 0.70

- (ii) Participants ≥ 12 years of age

The Cockcroft-Gault equation²⁷ will be used to estimate the creatinine clearance for participants ≥ 12 years of age.

$$\text{CrCl (ml/min)} = \frac{(\text{140} - \text{age}) \times \text{Body Weight (kg)}}{\text{Serum Creatinine (mg/dL)} \times 72} \quad (\times 0.85 \text{ if female})$$

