5. STUDY TREATMENTS

5.1. Dosing Scheme

Oral solution (1 mg/mL concentration) will be used for subjects weighing <40 kg. Oral tablets (5 mg) will be used for subjects weighing ≥40 kg; subjects who are unable to swallow tablets will have the option of taking oral solution.

Subjects will swallow study tablets whole and will not manipulate or chew tablets prior to swallowing.

Dosing cards with clear written instructions on how to properly take study medication will be provided to the parent/legal guardian/subject at the time study medication is dispensed.

Tofacitinib will be administered orally BID (twice daily) approximately 12 hours (± 2 hours) apart, once in the morning and once in the evening, based on body weight as provided in the Table 2 below. Body weight will be assessed at each visit and entered into Interactive Response Technology (IRT) system; study drug dose will be dispensed based on the subject body weight.

Table 2. Study Treatment Dosing and Administration

Body Weight (kg)	Dosage Regimen
5 - <7	2 mg (2 mL oral solution) BID
7 - <10	2.5 mg (2.5 mL oral solution) BID
10 - <15	3 mg (3 mL oral solution) BID
15 - <25	3.5 mg (3.5 mL oral solution) BID
25 - <40	4 mg (4 mL oral solution) BID
≥ 40	5 mg (one 5 mg tablet or 5 mL oral solution) BID

Important Note: For subjects rolling over from study A3921103 and actively participating in this study at the time of Protocol Amendment 6 and receiving a dosage of tofacitinib in accordance with the dosing scheme specified in Protocol Amendment 5 (see [Appendix 12](#)), investigators will have the option of maintaining the subject's current dosage regimen from index study A3921103 (if the desired clinical response has been attained with no safety concern) or adjusting the dosage regimen in accordance with the dosing scheme specified in this section.

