27-29	4.5mg (4 mL oral solution) BID
≥30	5 mg (one 5 mg tablet or 5 mL oral solution) BID

Subjects Completing Index Study A3921103 (Age 6 to <18 years)

Body Weight (kg)	Dosage Regimen
5-11	1 mg (1 mL oral solution) BID
12-18	1.5 mg (1.5 mL oral solution) BID
19-24	2 mg (2 mL oral solution) BID
25-31	2.5 mg (2.5 mL oral solution) BID
32-39	3 mg (3 mL oral solution) BID
≥40	5 mg (one 5 mg tablet or 5 mL oral solution) BID

Note: Investigators will have the option of maintaining the A3921103 subject's current dosage regimen (if the desired clinical response has been attained with no safety concern) or adjusting the dosage regimen in accordance with dosing scheme specified in [Section 5.1](#).

Appendix 13. By Visit Assessment of the Degree of Burden and Risk Threshold During the Trial (Investigative Sites in Belgium Only)

As written in the protocol under the [Schedule of Activities](#) and [Section 6](#) and here summarised, at each visit (initially at 1 month, 3 months, and every 3 months thereafter), the investigator will complete the following (including, but not limited to):

1. A medical history which includes at least one conversation regarding the child's wellbeing, generally at the beginning of the study and at each visit;
2. A physical examination including vital signs, growth, and maturation;
3. Laboratory testing, eg, haematology and liver enzymes, etc., and uveitis examination;
4. Various functional and global assessments depending on the child's specific rheumatologic diagnosis such as the JIA joint assessment, flare assessment CHAQ, and the CHQ; the Physician's Global Evaluation of Overall Disease Activity, the Tender Enthesal Assessment, Modified Schober's Test, Overall Back Pain and Nocturnal Back Pain Assessment for enthesitis related arthritis, psoriatic body surface area assessment; the Physician's Global Assessment (PGA) for psoriatic arthritis;
5. The investigator also will assess for flare and ACR responses using the JIA ACR Response and Flare Criteria provided in [Section 7.1.6](#) of this protocol;

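### Protocol Appendix 4 restarts tofacitinib at 5 mg BID and tapers it in 5 mg steps whatever the child's weight, which conflicts with the weight-based doses in Table 2 for most subjects under 40 kg

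*Protocol*

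**What the plan says.** Protocol Appendix 4 lets subjects reduce and stop treatment: "Subjects who have inactive disease for at least 24 consecutive weeks may begin to taper off of concomitant JIA therapies and tofacitinib". For tofacitinib the rule is "The dose is to be reduced by 5 mg every 12 weeks" while disease stays inactive, and "The evening dose should always be reduced before the morning dose". The only worked example starts from 5 mg BID: 10 mg/day falls to 5 mg/day (morning dose only), then to zero. If inactive disease is lost, treatment may resume at the investigator's judgment, and the dose is given as "Tofacitinib will restart at 5 mg BID".

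Section 5.1, Table 2, assigns 5 mg BID only at 40 kg or more. The 25-<40 kg row reads "4 mg (4 mL oral solution) BID"; the 15-<25 and 10-<15 kg rows give 3.5 and 3 mg BID. Weight is entered into the IRT at each visit, and "study drug dose will be dispensed based on the subject body weight".

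There is one exception. For A3921103 rollovers active at Amendment 6, "investigators will have the option of maintaining the subject's current dosage regimen from index study A3921103". Under Appendix 12, the scheme for ages 2 to <6 years reaches "5 mg (one 5 mg tablet or 5 mL oral solution) BID" from 30 kg.

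**The concern.** Appendix 4 is written in milligrams that suit only a subject on 5 mg BID, yet it applies to every subject who qualifies to taper. A site restarting a 20 kg child has two instructions: 3.5 mg BID from Table 2 and 5 mg BID from Appendix 4. Nothing says which prevails at a restart.

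Section 1.2.2 explains the lighter-weight doses: they were chosen to match average steady-state exposure in subjects of 40 kg or more on 5 mg BID, with Cmax not above that of 10 mg BID in most subjects. A restart that ignores weight departs from that rationale. It also collides with the protocol's own tolerance: Section 8.4 treats intake above 110% of the prescribed dose over a visit interval as a reportable deviation. If Table 2 is the prescribed dose, a site that obeys Appendix 4 exceeds that limit.

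The fixed taper step withdraws treatment faster from lighter children, although no reason is given for treating them differently.

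**Working it through.** **Inputs.** Doses are from Table 2; the restart dose and taper step are from Appendix 4. Table 1 (Section 1.2.2) gives AUC, Cmax and CL/F by cohort. The adult RA reference values on 5 mg BID, also in Section 1.2.2, are AUC 252 ng·hr/mL and Cmax 58 ng/mL.

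**The plan's own example.** 2 × 5 = 10 mg/day; 10 − 5 = 5; 5 − 5 = 0. It reproduces.

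**The same rules applied to the other bands.** Restart ratio = 5 / Table 2 dose. Remaining after the first step = (2 × dose − 5) / (2 × dose).

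| Weight (kg) | Table 2 dose (BID) | Restart ratio | Daily dose after first 5 mg step | Remaining |
|---|---|---|---|---|
| ≥40 | 5 mg | 1.00 | 10 → 5 mg | 50% |
| 25-<40 | 4 mg | 1.25 | 8 → 3 mg | 37.5% |
| 15-<25 | 3.5 mg | 1.43 | 7 → 2 mg | 28.6% |
| 10-<15 | 3 mg | 1.67 | 6 → 1 mg | 16.7% |

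Below 40 kg the first step takes the whole evening dose plus 1, 1.5 or 2 mg of the morning dose. The 1 mg/mL solution makes this feasible, but it is not the one-dose-at-a-time pattern of the example. Bands under 10 kg are assumed empty; there a 5 mg step would stop the drug outright (4 → 0 and 5 → 0 mg/day). The same holds for any retained Appendix 12 regimen of 2.5 mg BID or less.

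**Exposure after a literal restart, Cohort 3 (13.9-19.8 kg, n = 9).** AUC at dose D = D / (CL/F). Geometric mean dose given = 142.5 × 20.53 = 2,926 µg, or 2.93 mg. Cmax per mg = 66.15 / 2.926 = 22.6 ng/mL. Dose-proportional scaling is assumed; the population PK model in Section 1.2.2 has linear elimination.

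- 5 mg: AUC 5000 / 20.53 = 243.5; Cmax 113.1.
- 3.5 mg: AUC 170.5; Cmax 79.1.
- 3 mg: AUC 146.1; Cmax 67.8.

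Against adults on 5 mg BID, 243.5 / 252 = 0.97. Against Cohort 1 (38.3-70.9 kg) at 5 mg, AUC is 5000 / 28.09 = 178.0, and 243.5 / 178.0 = 1.37.

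**Cmax reference.** The 10 mg BID value is not given; assume 2 × 58 = 116 ng/mL. With lognormal spread, P(Cmax > 116) = 1 − Φ(ln(116 / mean) / s), where s = √ln(1 + CV²). The Table 1 CV of 28% gives s = 0.275.

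| Dose | Mean Cmax (ng/mL) | Share above 116, CV 28% | Range for CV 20-40% |
|---|---|---|---|
| 5 mg | 113.1 | 46% | 45-47% |
| 3.5 mg | 79.1 | 8% | 3-16% |
| 3 mg | 67.8 | 2.5% | 0.3-8% |

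**Cohort 2 (20.3-48.9 kg) at 5 mg.** AUC 5000 / 25.48 = 196.2. Geometric mean dose = 118.8 × 25.48 = 3.027 mg, so Cmax = 41.67 / 3.027 × 5 = 68.8. Both are well below the references of 252 and 116, so the peak-concentration question is confined to the lightest children.

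**The exception.** Only A3921103 subjects on the 2 to <6 years scheme can hold 5 mg BID below 40 kg. Cohort 3 had 9 such subjects, so at most 9 / 340 = 2.6% of projected enrollment, and each would have had to grow to 30 kg.

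**The case against.** The best reply is that 5 mg BID is the protocol's label for the whole weight-based regimen. Sections 1.2.2 and 2.3.2 use it that way, and Section 7.2.10 says that subjects with a thromboembolism risk factor may remain on 5 mg BID, which makes little sense if lighter children are excluded. The dispensing rule in Section 5.1 is general, is repeated for children under 40 kg in Section 7.2.7, and does not exempt restarts. On this view the IRT would issue the Table 2 dose.

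That is a real mitigation, but it does not settle the matter. The sentences just before the restart instruction speak of a 10 mg total daily dose and of 5 mg in the morning with none in the evening. Those are literal amounts. A general dispensing rule also does not plainly override a specific restart instruction.

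On exposure, the objection largely stands. AUC after a literal restart does not exceed the adult 5 mg BID value. Even at 5 mg, slightly more than half of the lightest children stay below the assumed 10 mg BID reference, which is a single adult summary value.

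On the taper, the 50% cut comes from an example rather than a stated rule, and treatment can resume at any time.

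The number affected is probably small. A3921103 and A3921104 participation ends after the first pJIA approval in any country (Section 3), and Section 1.1 reports US and EU approval. Any remaining subject must reach sustained inactive disease, taper, relapse and weigh under 40 kg.

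**Conclusion.** The concern holds. As written, Appendix 4 gives subjects of 10 to <40 kg a restart dose 25% to 67% above Table 2, apart from the few A3921103 rollovers who may already hold 5 mg BID. Its first taper step removes 62.5% to 83.3% of their daily dose instead of 50%.

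The dose arithmetic needs no assumptions. The Cmax comparison rests on dose proportionality, a lognormal spread, a doubled adult value and nine subjects, so it should be read as approximate parity with 10 mg BID in the lightest children, not as a demonstrated breach.

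The documents do not give the number of subjects affected. No endpoint definition or analysis in the SAP changes. This is a dosing-instruction conflict in a pediatric protocol: it should be fixed, but it does not threaten the study's conclusions.

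**What to change.** Replace two sentences in Appendix 4.

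- **Restart:** Tofacitinib will restart at the Table 2 dose for the subject's current body weight, or at the subject's prior Appendix 12 regimen if that was kept.
- **Taper:** The full evening dose is dropped first; after at least 12 consecutive weeks of continued inactive disease on the morning dose alone, the morning dose may also be stopped.

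The 10 → 5 → 0 example is unchanged, and the lighter bands follow the same pattern (8 → 4 → 0, 7 → 3.5 → 0, 6 → 3 → 0 mg/day). Also confirm that the IRT taper and restart settings match the new text.

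The cost is a protocol clarification letter, or two lines in the next amendment, plus the IRT check. No new data are needed.

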Appendix 6. Prohibited Concomitant Medications

All prohibited drugs require a 4 week (≥ 5 half-lives) washout, except:

* **Amiodarone** half-life averages about 58 days and requires a 290 day washout (5 half-lives);

** **Biologic DMARDs** which have specific washout periods listed in [Appendix 1](#).

NOTE: Topical administration (eg, cutaneous, ophthalmic, or intravaginal) of listed concomitant medications, which are prohibited if administered systemically, is allowed in the study.	
Moderate or Potent CYP3A Inhibitors	Moderate or Potent CYP3A Inducers
HIV antivirals:	efavirenz (Sustiva)
-delavirdine (Rescriptor)	nevirapine (Viramune)
-indinavir (Crixivan)	Barbiturates
-nelfinavir (Viracept)	carbamazepine (Carbatrol, Tegretol)
-ritonavir (Kaletra, Norvir)	modafinil (Provigil)
-saquinavir (Fortovase)	Phenobarbital
-atazanavir	phenytoin (Dilantin, Phenytek)
amiodarone (Cordarone, Pacerone)*	rifabutin (Mycobutin)
cimetidine (Tagamet)	rifampin (Rifadin, Rifamate, Rifater)
clarithromycin (Biaxin, Prevpac)	rifapentine (Priftin)
telithromycin (Ketek)	St. John's Wort
Clotrimazole	troglitazone (Rezulin)
Chloramphenicol	All Investigational Drugs
diethyl-dithiocarbamate	DMARDs
diltiazem (Cardizem, Tiazac)	All Biologics** , such as: anakinra (Kineret), etanercept (Enbrel), adalimumab (Humira), infliximab (Remicade), abatacept (Orencia), canakinumab (Ilaris), tocilizumab
erythromycin	
fluconazole (Diflucan)	

fluvoxamine (Luvox)	(Actemra), golimumab (Simponi), rituximab (Rituxan), baricitinib (Olmiant), certolizumab (Cimzia), secukinumab (Cosentyx).
Grapefruit juice and marmalade	
itraconazole (Sporanox)	
ketoconazole (Nizoral)	Other DMARDs**: d-penicillamine, bucillamine, mizoribin, azathioprine, cyclosporine, tacrolimus, auranofin, aurothioglucose, aurothiomalate, staphylococcal protein A immuno-absorbant pheresis columns and Immunoglobulin IV.
mifepristone (Mifeprex, RU486)	
nefazodone (Serzone)	
norfloxacin (Shibroxin, Noroxin)	
mibefradil	
verapamil (Calan SR, Covera HS, Isoptin SR, Tarka, Verelan)	
Voriconazole	

Appendix 7. Rescue Therapy

Acetaminophen/paracetamol is allowable as rescue medication if dosed no more than 10-15 mg/kg/dose orally or 15-20 mg/kg/dose rectally (not exceeding 5 doses in 24 hours) for no more than 10 consecutive days. If a subject is already taking stable background doses of acetaminophen/ paracetamol, (s)he may increase the dose up to the maximum dose stated above for up to 10 consecutive days for rescue purposes.

The following paradigm should be used to determine appropriate opioid rescue therapy:

For patients who are NOT on stable, background opioid therapy: any of the following single opioid agents may be given as rescue medication (with or without acetaminophen/ paracetamol) for no more than 10 consecutive days in the following total daily doses:

Morphine	0.2-0.5 mg/kg/dose, up to 15 mg/dose. No more than 5 doses/day.
Hydromorphone (Dilaudid)	0.03-0.08 mg/kg/dose, up to 2 mg/dose. No more than 5 doses/day.
Codeine (Paveral, Tylenol #2 and #3)	0.5-1.0 mg/kg/dose, up to 60 mg/dose. No more than 5 doses a day.
Oxycodone (Roxicodone; Percocet, Tylox)	0.05-0.15 mg/kg/dose, up to 5 mg/dose. No more than 5 doses a day.

For patients who ARE on stable, background opioid therapy:

- They may NOT add a second opioid agent for rescue.
- If their background medication is 1 of the 4 listed above, they may, within the above maximum total dosage limits, increase the dosage for up to 10 consecutive days for rescue purposes.
- If their background medication is a short-acting (half-life <5 hrs, [Appendix 2](#)) opioid that is not one of those listed above, they may increase the dosage for up to 10 consecutive days (up to a total daily dose which must not exceed the potency equivalent of 30 mg of orally-administered morphine [Appendix 2](#)) for rescue purposes.
- Sustained release opioid formulations (eg, OxyContin®, MS Contin®) and opioids with half lives greater than 5 hours (eg, methadone, propoxyphene) may NOT be USED for rescue medication or increased for rescue purposes.

Intravenous or intramuscular corticosteroids, biologic response modifiers and DMARDs other than those specified as allowed DMARDs ([Appendix 1](#)) are not allowed during this study. Intra-articular corticosteroids (eg, triamcinolone (KENALOG[®], Aristospan[®])) may be given in no more than four joints in a six month period. Injections should be avoided for 6 weeks before any study visit. Injected joints will also be considered as not assessed for the remainder of the trial

Acetaminophen/paracetamol is not permitted as a part of combination products such as over-the-counter “cold remedies” or in combination with opioids if the acetaminophen/paracetamol dose will exceed 2.6 gm/day. Subjects who require rescue for more than 10 consecutive days should be considered for allowed JIA medication adjustments or discontinued from the trial. In addition, subjects should not be dosed with rescue acetaminophen/paracetamol or opioids during the 24 hours prior to a study visit. Baseline stable acetaminophen/paracetamol or opioids should NOT be discontinued in advance of study visits.

Subjects should not be dosed with any rescue intervention within 24 hours prior to a study visit unless indicated for subject safety and individual case management at the discretion of the investigator.

